6.2.2 Specific considerations on the use of enrollment data

Children will be enrolled in the cohort 1 at the age of 6 months, when the program foresees MUAC screening measurements and inputs distribution to start. However, community care groups in the intervention study arms are tasked to conduct home visits to pregnant and lactating women and caregivers of children up to 24 months of age to provide BCC on child nutrition, health and WASH.

Therefore, it is likely that caregivers with children of 6 months enrolled in the cohort after the start of the program have been exposed to BCC prior to study inclusion in the intervention group. Similarly, it is likely that children enrolled in cohort 3 after the start of the program have been exposed to BCC, MUAC screening or inputs distribution prior to study inclusion in the intervention group. For this reason, all longitudinal analyses of cohort 1 and cohort 3 data will include the data at enrollment as impact data, and analyses studying impacts at exit will not control for enrollment value of the outcome. For study outcomes related to activities that only start between the age of 6 and 7 months, like MUAC-based screening and the distribution of inputs, we will consider data related to the program's impact from the child age of 7 months onwards.

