3.4 Study outcomes

3.4.1 Primary study outcomes

For this study, wasting will be defined by $WHZ < -2$ (relative to the WHO reference of 2006) or $MUAC < 125$ mm or bilateral edema. Moderate wasting (MAM) will be defined by $-3 \leq WHZ < -2$ (relative to WHO reference of 2006) or $115 \leq MUAC < 125$ mm. Severe wasting (SAM) will be defined by $WHZ < -3$ (relative to WHO 2006 reference) or $MUAC < 115$ mm or bilateral edema.

The primary outcomes of the study will be:

1. Longitudinal prevalence of wasting among children enrolled at 6 months of age followed monthly until the end of the study (cohort 1). This indicator is defined for each child as the number of visits during which wasting is observed divided by the total number of monthly visits made (by interviewers).

⁴ Gould, W. W. 2012a. Using Stata's random-number generators, part 2: Drawing without replacement. The Stata Blog:

Not Elsewhere Classified. <http://blog.stata.com/2012/08/03/using-statas-random-number-generators-part-2-drawing-without-replacement/>.

2. The recovery rate in children enrolled at [6-23] months of age for up to 3 months of treatment in a treatment unit and followed through to discharge (cohort 2). This indicator was initially defined in the protocol as the number of discharges considered cured according to national program criteria (WHZ>-2 and MUAC>=125mm and absence of bilateral edema for two consecutive visits, within 12 weeks of enrollment in the program) divided by the total number of exits recorded. Due to COVID-19 modifications in the implementation of the national protocol, children are discharged based on the MUAC criteria only, after only one visit, and WHZ is not measured. We therefore redefined this indicator as the number of discharges with MUAC>=125mm within 12 weeks of enrollment in the program, divided by the total number of exits recorded.
3. The incidence of wasting in children enrolled at [6-23] months of age at discharge from a wasting treatment program and followed for 6 months (Cohort 3). This indicator is defined as the number of new cases of wasting recorded during monthly visits.

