3.4.2 Secondary study outcomes

Secondary outcomes of the study include:

For Cohorts 1 and 3 :

- The longitudinal prevalence of :
 - Wasting, defined as above (cohort 3)
 - MAM, defined for each child as the number of MAM diagnoses divided by the total number of monthly visits made
 - SAM, defined for each child as the number of SAM diagnoses divided by the total number of monthly visits made
- The incidence of :
 - Wasting, defined as above (cohort 1).
 - MAM, defined as the number of new MAM cases recorded during monthly visits.
 - SAM, defined as the number of new SAM cases recorded during monthly visits.
- The prevalence of anemia defined as the proportion of children with a hemoglobin level below 11g/dl at the end of the study.
- Mean hemoglobin concentration at the end of the study.
- Prevalence of stunting defined as the proportion of children with HAZ <-2 (relative to the 2006 WHO reference) at the end of the study.
- The average z-scores HAZ at the end of the study.
- Wasting screening coverage defined as the proportion of children screened (using MUAC, weight-for-height or bilateral edema) in the month prior to the monthly visit. Two sub-outcomes will also be considered:
 - Screening coverage by care groups.
 - Screening coverage of the family MUAC component, which is the screening performed by a family member in the past month.
- Linear growth rate defined as the change in height-for-age index per month.
- Speed of weight growth defined as the change in weight-for-height index per month.
- Weight gain defined as the weight change per month.
- MUAC gain defined as the change in MUAC per month.

- The longitudinal prevalence of childhood morbidity, i.e. acute respiratory infections, fever, diarrhea and malaria, defined as the number of reports of signs of these morbidities divided by the total number of days reported (1-3 per monthly visit made).
- Mother/guardian's knowledge of nutrition, WASH, and health expressed as cumulative total and domain scores at exit.
- Infant and young child feeding (IYCF) practices:
 - Introduction of (semi) solid and soft complementary foods .
 - Minimum dietary diversity in children, defined as the proportion of children who consumed at least 5 of the 8 food groups (including breast milk) the day before the survey.

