3.6 Sampling and study inclusion criteria

Details on the selection of children, inclusion and exclusion criteria, and changes to the protocol, are given in Table 2.

Table 2: Selection of study participants, inclusion and exclusion criteria, sample size and follow-up details for the 3 study cohorts.

	Main cohort	Treatment cohort	Relapse prevention cohort
Selection of participants	In each village, random selection from a randomly ordered census list of children aged 0-6 months (census conducted by the survey team in the first month of the survey), prepared by an investigator based in Dakar using Stata software. Children not meeting inclusion criteria (see below) will be replaced until the maximum number of children is met (3 times the number of months of inclusion), or until the list of eligible children is exhausted.	All records of children (aged [6-23] months) living in the 100 most populated villages in the study area and admitted during the study in a treatment program by the national CMAM program. Treatment data will be collected by the CMAM treatment units as part of their routine. Each treatment unit will be visited by an enumerator who will be responsible for monitoring data quality and copying anonymous data from the registers to electronic forms.	All available children in each village who will be discharged from CMAM treatment (based on treatment unit registers) and recovered will be invited to participate in the study until the required sample size is reached for each village (8 children). In villages with more children than necessary, the study team will invite children to participate in the order of a randomly ordered list prepared by an investigator based in Dakar using Stata software.
Inclusion criteria	6-6.9 months of age. Child singleton. Resident of the village. Consent of the mother or guardian.	Child admitted for treatment in a national treatment program. 6-23 months of age at admission. Child lives in one of the 100 villages in the study area.	Child has been successfully treated for wasting (defined as MUAC ≥ 125 mm) and has been discharged from the national treatment program within the last 30 days. 6-23 months of age at inclusion. Child singleton.

	Main cohort	Treatment cohort	Relapse prevention cohort
			Resident of the village. Consent of the mother or guardian.

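### In cohort 3, the enrolment visit dilutes overall screening coverage, because its one-month look-back contains the discharge MUAC and the 7-month age rule does not remove it

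*SAP*

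**What the plan says.** Four parts of the SAP bear on this point.

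- **Which visits count (6.2.2).** The general rule is that "all longitudinal analyses of cohort 1 and cohort 3 data will include the data at enrollment as impact data". For outcomes tied to activities that begin between 6 and 7 months of age, MUAC screening among them, the SAP makes one exception: "we will consider data related to the program's impact from the child age of 7 months onwards". The exception is defined by the child's age, not by the visit.
- **Who enters cohort 3 (Table 2).** A child must be "6-23 months of age at inclusion", must have recovered with MUAC of at least 125 mm, and "has been discharged from the national treatment program within the last 30 days". Section 3.4.1 adds that, under the COVID-19 modifications, "children are discharged based on the MUAC criteria only, after only one visit, and WHZ is not measured".
- **The outcome (3.4.2 and 5.1).** The definition for cohorts 1 and 3 reads "Wasting screening coverage defined as the proportion of children screened (using MUAC, weight-for-height or bilateral edema) in the month prior to the monthly visit". Section 5.1 makes this operational as the caregiver's recall that the child's MUAC was measured. It does not restrict who measured it or for what purpose. Screening by care groups and by a family member are two separate sub-outcomes.
- **The model (6.4.1 and 6.4.3).** Binary longitudinal outcomes are analysed with linear probability mixed models, with a child random intercept and a random slope on months since enrolment. Cohorts 1 and 3 are also pooled for secondary outcomes.

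**The concern.** The eligibility window and the look-back window are almost the same. A child included in cohort 3 had a MUAC reading at a treatment unit at most 30 days earlier, and the enrolment interview asks about the preceding month. Under the 5.1 definition, a caregiver who recalls the discharge measurement reports a screened child, in either arm. For overall coverage, this visit then mainly records that the child met the inclusion criteria. It says little about whether PASIM brought screening to the household.

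The SAP does have a safeguard for screening outcomes at enrolment, but it is built around the age at which the activities start. It does what is needed in cohort 1. In cohort 3 it removes only enrolment visits at 6.0-6.9 months, one of the 18 monthly age bands from 6 to 23.

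At stake is the size of the estimated effect on screening coverage in cohort 3. Screening coverage answers one of the protocol's secondary research questions (3.4). The distortion is systematic, so more data would not reduce it.

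**Working it through.** **The plan's own count.** SAP 3.5.3 gives 8 children in each of 50 villages and 6 in each of the other 50: 50 × 8 + 50 × 6 = 700. With one inclusion visit and six follow-ups each, 700 × 7 = 4,900 visits, of which 700 are inclusions and 4,200 follow-ups. This agrees with the SAP. The documents give no expected screening coverage, target difference or power for this outcome, so there is nothing further to reproduce.

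**Share of enrolment visits, s.**

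- Planned: s = 700 / 4,900 = 1/7 = 14.3%.
- Amended in January 2022 (Table 2: inclusion over 9 months, study of 12 months, follow-up for 6 months or to study end). Assume even monthly accrual from month 1, which the documents do not report. Children included in months 1-6 have 7 visits; those included in months 7, 8 and 9 have 6, 5 and 4. For one child per month the total is 6 × 7 + 6 + 5 + 4 = 57, so s = 9/57 = 15.8%.
- A child included in month 9: s = 1/4 = 25%.

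**Dilution.** Let d be the arm difference in coverage at each follow-up visit and e the difference at enrolment. With equal weight per visit, the averaged difference is

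D = (1 − s)·d + s·e.

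If enrolment coverage is the same in both arms, e = 0 and D = (1 − s)·d:

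| Schedule | s | D |
|---|---|---|
| Planned, 7 visits | 0.143 | 0.857 d |
| Amended, even accrual | 0.158 | 0.842 d |
| Included in month 9 | 0.250 | 0.750 d |

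The level of enrolment coverage drops out of D; only its equality across arms matters. If e is not zero but is smaller than d, the result is still diluted, by less.

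**Illustration (assumed rates).** Take follow-up coverage of 30% in control and 60% under PASIM, so d = 30 points, with s = 1/7.

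- Enrolment coverage 100% in both arms: control 1/7 + (6/7)(0.30) = 40.0%; PASIM 1/7 + (6/7)(0.60) = 65.7%; difference 25.7 points.
- Enrolment coverage 90% in both arms: 38.6% against 64.3%; difference again 25.7 points.
- Amended schedule, enrolment coverage 100%: 41.1% against 66.3%; difference 25.3 points.

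With assumed follow-up rates of 20% and 40%, the 20-point difference becomes 17.1 points under the planned schedule.

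**Effect of the planned model.** Equal weights correspond to a random intercept alone. A random slope on months since enrolment gives early visits more weight. With total variance at enrolment set to 1, intercept variance 0.1-0.3 and slope variance 0.005-0.02 (all assumed), the weight on the enrolment visit in a seven-visit series is about 0.20-0.29, so D falls to about 0.80-0.71 of d.

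If an arm-by-time term is fitted, a difference of 0 at month 0 and d at months 1-6 is read as a trend. The mean month is 3, Σ(t − 3)² = 28, and Σ(t − 3) over months 1-6 is 3. The slope is 3d/28 = 0.107 d per month and the fitted effect at enrolment is 6d/7 − 3 × 0.107 d = 0.54 d. The apparent growth in effect would come from the enrolment visit alone.

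**The case against.** **Enrolment coverage is unknown.** A reader might infer that it is known to be close to 100% in both arms. The documents do not say so. It follows only from combining eligibility with the definition, and it depends on recall and on questionnaire content that is not available. If the instrument already leaves out treatment-unit measurements, the problem disappears, though the SAP does not say that it does. This objection stands against the level. It does not remove the dilution, which needs only similar enrolment coverage in the two arms.

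**The definition cuts both ways.** If any recalled MUAC counts, then so does the survey team's own monthly measurement, which falls in the look-back of the next visit. Follow-up coverage would then also be pushed up in both arms, and an illustration such as 30% against 60% could not arise. This stands. It shows that the 5.1 definition needs a restriction on source, and that a visit rule alone would be an incomplete repair.

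**Enrolment data are kept on purpose.** Section 6.2.2 retains them because cohort 3 children may already have been reached by BCC, screening or inputs before inclusion. That is a sound reason for other outcomes and for the two sub-outcomes. It does not meet this point: for overall coverage, the discharge reading masks whatever earlier community or family screening took place.

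**Scope.** A reader might extend the point to the care-group and family-MUAC sub-outcomes. A discharge reading at a treatment unit is neither, so their enrolment data remain usable. A reader might also express the loss as a coverage ratio, which looks larger, but the planned linear probability model estimates a difference. Cohort 1, the experimental cohort, is protected by the age rule in its own analysis.

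**Conclusion.** The point holds for overall screening coverage in cohort 3, and for the cohort 3 records in the pooled analysis. Applied as written, 6.2.2 keeps a visit at which coverage is largely determined by eligibility. The averaged risk difference is then about 14% smaller than its follow-up value under the planned schedule, or about 16% smaller under the amended schedule.

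These figures assume similar enrolment coverage in both arms, a constant follow-up difference and equal visit weights; the second also assumes even accrual. The random slope could make the loss larger, but by how much depends on variances that the documents do not give.

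The severity is minor. The bias is moderate and towards the null, it affects one secondary outcome, and the SAP itself (3.2) calls this cohort quasi-experimental. With equal enrolment coverage, the average effect carries no added risk of a false positive. A stronger claim, that the cohort 3 screening result is invalid or that a known ceiling exists at enrolment, is not supported.

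**What to change.** 1. In SAP 6.2.2, for overall screening coverage in cohort 3 and in the pooled cohort 1 and 3 analysis (6.4.3), replace reliance on the age rule with a visit rule: use data from the first follow-up visit onward.
2. In SAP 5.1, state that MUAC taken at treatment or discharge visits, or by the survey team, does not count as screening. If the questionnaire already makes this distinction, say so.
3. Keep cohort 3 enrolment data for the care-group and family-MUAC sub-outcomes.

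The cost is a few sentences of SAP text and about 14-16% of cohort 3 records, for the overall coverage outcome only. Those records carry little information on the arm difference. The visit rule needs no new data, since the planned models already use months since enrolment. The source restriction can be applied to collected data only as far as the questionnaire recorded who took the measurement; where it did not, report that as a limitation.

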While the main cohort study is an experimental study³, the treatment cohort and relapse prevention study are quasi-experimental in nature. The quasi-experimental character of these two sub-studies implies the random character of the intervention and comparison group is not fully guaranteed. More precisely, children enrolled in the treatment cohort may not be comparable between study groups because the BCC and food supplement may prevent a proportion of the usual prevalence of wasting. Similarly, a higher screening coverage or screening by family MUAC may refer children with wasting with different characteristics as compared to those in the comparison group. Therefore, any impact or lack of impact of the intervention to support the CMAM services need to be interpreted with caution, as it may be a result of both the intervention and any different characteristics of the enrolled samples of children. For the same reasons, the results of the relapse prevention study must be interpreted bearing in mind possible impacts of the preceding preventive BCC and food supplement and improved screening and referral (studied in the main cohort), as well as possible impacts on the adherence and recovery rates of CMAM services (studied in the treatment cohort).

³ The main cohort study is an experimental cluster-randomized controlled study that guarantees (if random allocation of clusters is successful) that the samples of children enrolled in the intervention and comparison group have similar household, caregiver, and child characteristics. Therefore, any observed impacts can be exclusively associated with the intervention.

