During follow-up visits, we will interview the caregiver about child morbidity (acute respiratory infections, diarrhea, fever, and malaria) over the previous 3 days. Diarrhea will be defined as recall of at least three loose stools in 24 hours, or of stools with blood. Fever (axillary temperature $> 37.5^{\circ}\text{C}$) will be measured by a thermometer and the history of fever for each of the 3 previous days will also be recalled. The presence of an acute respiratory infection (ARI) in the 3 previous days will be assessed by recalling the specific symptoms associated with ARI (cough, difficulty breathing, rapid breathing, wheezing). The presence of malaria parasites will be checked by enumerators with a rapid diagnostic test for malaria, if body temperature is above 37.5°C or if the mother reports a fever episode in the child within the last 72 hours.

The hemoglobin concentration will be measured at enrollment and at exit by spectrophotometry using a HemoCue 301 (HemoCue Ltd, Dronfield, UK), using a drop of capillary blood drawn from the child's finger.

Child anemia and severe anemia will be defined by hemoglobin concentrations of less than 11 g.dL⁻¹ and less than 7 g.dL⁻¹ respectively.

Screening will be defined as caregiver recall that MUAC was measured in the target child.

Single treatment coverage will be calculated at individual level on the sub-group of children with wasting and children recovering from wasting, using the formula:

$$\text{single coverage} = \frac{C_{in} + R_{in}}{C_{in} + R_{in} + C_{out} + R_{out}}$$

where C_{in} = current wasting, SAM or MAM cases under treatment, C_{out} = current wasting, SAM or MAM cases not under treatment, R_{in} = recovering wasting, SAM or MAM cases under treatment, and R_{out} = recovering wasting, SAM or MAM cases not under treatment. Children with wasting and recovering children will be identified using the anthropometric measures. Recovering children will be defined as children with wasting the previous month but not wasted the current month.

Principal component analysis will be used to generate a household wealth status score (17). We will include household-level data on materials used in housing roofs, floors, and walls, occupational status of the housing, the main source of light, and assets owned by 5 to 95% of the study sample at enrollment. Tertiles of loadings on the principal component with the highest eigenvalue will be used.

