6.1 Guiding principles and analysis strategy

Data will be analyzed on intent-to-treat basis. To allow for an analysis “as randomized” in the presence of missing data, we will impute missing data of the primary outcomes of the longitudinal study using a multiple imputation strategy under the *missing at random* assumption (see section 6.3 below). Data management, data cleaning, and statistical analyses will be done using Stata 17.0 (Statacorp, USA). The statistical significance will be set at 5%. All statistical tests will be two-sided. The analysis of primary study outcomes will not be adjusted for multiple testing (n=3 primary study outcomes) given the data involved represent three distinct experimental and control study samples with each one primary study outcome.

We will present results from non-adjusted and adjusted linear mixed effects regression models.

The non-adjusted models to analyze cohort 1 and 3 data will use *village (cluster)* as a random intercept and sampling stratum as a fixed effect to represent the study design. The non-adjusted models to analyze cohort 2 data will include sampling stratum as a fixed effect and will use a random intercept at the health center level and a random slope at the village level, to account for nesting of villages (clusters) into health centers (where treatment occurs for children from several villages).

In addition, we will conduct adjusted analyses, adjusting for the following variables:

- covariates that appear imbalanced at enrollment (absolute difference >10 pp) and are unlikely to have been impacted by exposure to the intervention before 6 months of age (cohort 1 and 3; virtually no household, parental or sociodemographic child level data collected at admission in cohort 2).
- child sex, and whether child was the first live birth, since a recent meta-analysis has reported that imbalance in child nutritional status between study groups can be associated to the imbalance in child sex and primiparity (3) (all adjusted models, except that data on first live birth are missing for cohort 2).
- month of enrollment (longitudinal models, cohorts 1 and 3) or month of admission into treatment (cohort 2).
- Child age at enrollment (cohort 3; constant in cohort 1; not detailed in MAM treatment registers used for cohort 2).
- type of nutrition unit where the child is/was treated (cohorts 2 and 3).

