6.2 Enrollment characteristics

6.2.1 Characteristics of study groups at enrollment

The presentation of enrollment characteristics (see Table 3) will be done as follows:

- Categorical variables: frequencies and percentages, as appropriate. Percentages will be calculated based on the number of participants for whom data are available.
- Continuous variables: mean and SD or median and interquartile range, as appropriate.

Following the CONSORT guidelines, we will not statistically test for differences between study groups at enrollment in cohort 1 (18). Imbalance will be considered for absolute differences >10 pp (binary

outcomes) or >10 % (continuous outcomes). However, as the intervention risks impacting the size and characteristics of the study population for cohort 3 (if it impacts who is wasted, and then treated and cured from wasting), we will test baseline differences across groups in cohort 3, using linear (continuous outcomes) and linear probability (binary outcomes) mixed-effects regression models with robust estimation of standard errors, considering the cluster as a random effect, and strata and intervention as a fixed effect.

Table 3: Enrollment characteristics for cohorts 1 and 3

Characteristics	Comments/References
Household level	
HH size (mean/SD)	
Number of under 5 children in household (mean/SD)	
Number of adults (15-64 y) (mean/SD)	
Polygamous HH(%)	
HH food insecurity (mean and proportion of food secure HH)	Coates J, Swindale A, Bilinsky P. Household Food Insecurity Access Scale (HFIAS) for measurement of food access: indicator guide. Washington, DC: FANTA; 2007. https://doi.org/10.1007/s13398-014-0173-7.2
SES status classification (tertiles, %)	Principal component analysis will be used to construct a proxy household Socio-Economic Score (SES) using ownership of various assets (an asset is excluded if ownership is below 5% or above 95% on HH level), housing materials, primary source of lighting, primary energy source, and home ownership. Tertiles of the first principal component (i.e., the one with the highest eigenvalue) will be used.
Improved water treatment technologies used (%)	USAID (2021) Water and development- Indicator handbook. Washington DC
Improved sanitation facility (%)	USAID (2021) Water and development- Indicator handbook. Washington DC
Handwashing station with soap available (%)	USAID (2021) Water and development- Indicator handbook. Washington DC

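### Cohort 3 exit outcomes: with no enrollment-adjusted estimate beside the planned one, selection, earlier exposure and the effect after discharge cannot be told apart, chiefly for haemoglobin and anaemia

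*SAP*

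**What the plan says.** - SAP 6.2.2 sets one rule for both home-visit cohorts: enrollment data count as impact data, and "analyses studying impacts at exit will not control for enrollment value of the outcome". The reason given for cohort 3 is probable earlier exposure: "children enrolled in cohort 3 after the start of the program have been exposed to BCC, MUAC screening or inputs distribution prior to study inclusion".
- SAP 3.2 says that "the treatment cohort and relapse prevention study are quasi-experimental in nature" and asks for caution in reading them: "the results of the relapse prevention study must be interpreted bearing in mind possible impacts" of the earlier prevention, screening and treatment activities.
- SAP 6.2.1 adds that "the intervention risks impacting the size and characteristics of the study population for cohort 3", through who is wasted, treated and cured, so "we will test baseline differences across groups in cohort 3". It does not say what follows if a difference is found.
- SAP 6.1 plans adjusted models. For cohort 3 they include sex, first live birth, month of enrollment, age at enrollment, type of nutrition unit, and "covariates that appear imbalanced at enrollment (absolute difference >10 pp) and are unlikely to have been impacted by exposure to the intervention"; the SAP limits that exposure to the first 6 months of life.
- SAP 3.4.2 lists anaemia, mean haemoglobin, stunting and mean HAZ at the end of the study as secondary outcomes, and HAZ change per month separately. SAP 6.4.1 plans growth-curve models with an arm-by-visit interaction for continuous anthropometry and treats stunting as a cross-sectional exit outcome.
- SAP 5.1: "The hemoglobin concentration will be measured at enrollment and at exit by spectrophotometry". SAP Table 3 lists length-for-age, stunting, haemoglobin and anaemia at enrollment for cohort 3.
- SAP 6.4.3 contains no exit analysis that uses the enrollment value.

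**The concern.** In cohort 1 the rule is coherent. Villages were randomised, so an enrollment gap is either chance or an early effect of the package, and controlling for it could remove effect.

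In cohort 3 there is a third source. Children enter only after becoming wasted, being detected, being treated and recovering, and the package may act on each step. Earlier exposure therefore explains only part of an enrollment gap; the rest may be selection, which the reason in 6.2.2 does not address. An uncontrolled exit comparison carries both forward together with the effect after discharge.

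Nothing else in the plan deals with the starting level of the outcome itself. The adjusted models use other covariates, and the 6-month wording in 6.1 does not fit children who may have been exposed up to 23 months of age. If the enrollment tests show a difference, any adjustment chosen then would be driven by the data.

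**Working it through.** **1. The plan's own figures.** Cohort 3: 50 × 8 + 50 × 6 = 700 children; 700 × 7 visits = 4,900. Both reproduce. The documents give no SD, enrollment-to-exit correlation, ICC, power or expected selection gap for any cohort 3 exit outcome, so what follows rests on assumptions.

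**2. Which exit outcomes have an alternative that uses the starting level?**

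| Exit outcome | Alternative already planned |
|---|---|
| Mean HAZ | HAZ change per month; arm-by-visit term |
| Stunting | Indirect only, through HAZ |
| Mean haemoglobin | None |
| Anaemia | None |

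**3. HAZ, uncontrolled.** Assumptions: 600 children (close to 700 × 0.85 = 595, borrowing the 15% dropout stated for cohort 1), 6 per village, ICC 0.05 (stated for cohort 2 only), SD 1.2, and no effect after discharge.

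Design effect = 1 + 5 × 0.05 = 1.25. Effective n per arm = 300/1.25 = 240. SE = 1.2 × √(2/240) = 0.110.

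P(significant) = Φ(b/SE − 1.96) + Φ(−b/SE − 1.96), where b is the bias at exit.

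**4. HAZ with the enrollment value in the model.** SE is multiplied by √(1 − ρ²), which is 0.60 at ρ = 0.8 and 0.44 at ρ = 0.9, giving 0.066 and 0.048. If the gap d persists fully to exit, the bias left is (1 − ρ)d.

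| Selection gap d | Uncontrolled | Adjusted, ρ = 0.9 | Adjusted, ρ = 0.8 |
|---|---|---|---|
| 0.1 z | 15% | 6% | 6% |
| 0.2 z | 45% | 7% | 9% |
| 0.3 z | 78% | 10% | 15% |

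If no village clustering is left in the residual, the adjusted figures at 0.2 z are about 8% and 10%; hence roughly 7-10% overall. If the gap instead regresses to ρd at exit with ρ = 0.8, the uncontrolled figures fall to 11%, 31% and 59%.

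**5. HAZ precision.** For a true 0.15 z effect with balanced arms:
- Uncontrolled: 0.15/0.110 gives power of about 28%.
- Adjusted: 0.15/0.066 gives 63% and 0.15/0.048 gives 88%.
- If no village clustering remains in the residual, SE = 1.2 × √(1 − ρ²) × √(2/300) = 0.059 or 0.043, and power is 72% or 94%. I use 63-88%, because nothing in the documents supports dropping the clustering.

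**6. Haemoglobin and anaemia.** In SD units: 700 children, 15% dropout, 5.95 per village, ICC 0.05. Design effect = 1 + 4.95 × 0.05 = 1.25; effective n = 297.5/1.25, about 238 per arm; SE = √(2/238) = 0.092 SD. Here the gap is taken to regress to ρd.

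| | ρ = 0.3 | ρ = 0.5 |
|---|---|---|
| Carry-over of a 0.2 SD gap | 0.06 SD | 0.10 SD |
| P(significant), no effect after discharge | 10% | 19% |
| Spurious anaemia difference at 30-50% prevalence | 2.1-2.4 points | 3.4-4.0 points |
| SE ratio with adjustment | 0.95 | 0.87 |
| Detectable difference (0.26 SD unadjusted) | 0.25 SD | 0.22 SD |

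**7. What adjustment would take away.** If the enrollment gap is a real earlier effect of 0.2 SD, adjustment removes ρ × 0.2 = 0.06, 0.10 or 0.16 SD at ρ = 0.3, 0.5 or 0.8.

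**The case against.** The SAP has a reason for its rule. Cohort 3 enrollment values may already be affected by the package, so conditioning on them can remove real effect and changes the question to what happens after discharge. The later extension of cohort 3 inclusion to 9 months (SAP Table 2) makes earlier exposure more likely. This stands, and it is why the planned contrast should be kept rather than replaced.

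A reader might infer that the plan would present selection differences as impact. The documents do not support that. SAP 3.2 calls the cohort quasi-experimental and asks for cautious reading, Table 3 displays the enrollment values, and the adjusted models cover some plausible routes of selection (age, month of enrollment, nutrition unit). A caution, however, neither estimates the selection component nor removes it, and none of those covariates is the starting level of the outcome.

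A reader might also infer a large loss of precision throughout. That depends on an unstated correlation: it could be large for HAZ and is modest for haemoglobin.

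Finally, growth after discharge is already estimated through HAZ change and the arm-by-visit term. This stands for HAZ and, less directly, for stunting. It does not help haemoglobin or anaemia.

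**Conclusion.** The point holds as a limited one. For cohort 3 exit outcomes the planned contrast combines three sources of difference, the SAP itself names selection as one of them, and no planned analysis uses the starting level for haemoglobin or anaemia.

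The false-signal risk for HAZ (about 45% against roughly 7-10% at a 0.2 z gap) and the power gain (28% to about 63-88%) depend on the assumed SD of 1.2, ICC of 0.05, correlation of 0.8-0.9 and, for the former, a gap that persists to exit. For haemoglobin the same concern is milder: 10-19% at a 0.2 SD gap, with a 5-13% smaller SE after adjustment. No selection gap is known to exist.

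It would go too far to say that this threatens the main cohort 3 result. The primary outcome, relapse incidence, is not an exit outcome, so the rule on exit analyses does not touch it; every affected outcome is secondary. Nor does the argument extend to cohort 1, where randomisation supports the rule. This is an inexpensive improvement, not a defect that invalidates the plan.

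**What to change.** In SAP 6.2.2:
1. Keep the uncontrolled exit contrast for cohort 3 and label it as the combined effect of selection, earlier exposure and follow-up.
2. Pre-specify beside it, for cohort 3 only, exit analyses of mean haemoglobin, anaemia, mean HAZ and stunting that add the continuous enrollment haemoglobin (first two) or enrollment HAZ (last two) as a covariate. Interpret these as the effect after discharge.
3. Report both whatever the enrollment tests in 6.2.1 show, so that the choice does not depend on their result.

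Leave cohort 1 unchanged.

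The cost is a few sentences and one covariate per model, all from data already collected. The adjusted estimate leaves out any real effect before discharge, and it may not remove all selection: in the HAZ example, 10-15% of trials were still significant at a 0.3 z gap. The text should state both limits.
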